## **13 SUBJECT LISTINGS**

All data that are collected and entered into the study database will be presented in subject listings by GEN-003-005 treatment group.

## **14 INTERIM ANALYSIS**

An interim analysis (IA) will be conducted after all subjects should have completed the Month 6 visit and will include analysis of lesion rates. The tables to be produced for this interim analysis are noted in the List of Statistical Tables Table of Contents (TOC) with an 'X' in the IA column.

## 16 REVISIONS TO STATISTICAL ANALYSIS PLAN

Date	Revision	Statistician's Signature
•	•	•
•	•	•
•	•	•
•	•	•
•	•	•
•	•	•

## 17 APPENDIX

### 17.1 Conventions for Statistical Tables and Listings

The following conventions are used in the mockups for the statistical tables:

[Sponsor] = [Genocea Biosciences]

[Protocol] = [GEN-003-005]

[Drug name] = [GEN-003]

In general, font size will be Courier 9-point and all margins will be 1 inch.

#### Treatment Groups

GEN-003 Antigens 60 µg / M2 50 µg

Placebo

**List of Statistical Tables for GEN-003-005**

Table No.	Table Title	Analysis Population	IA
14.1.1	Number and Percentage of Enrolled Subjects by Site and Treatment Group	Safety	
14.1.2	Demographic and Baseline Characteristics by Treatment Group	Safety	x
14.1.3	Summary of Analysis Populations by Treatment Group		
14.1.4	Subject Disposition by Treatment Group	Safety	
14.1.5	Frequency of Medical History Events by Treatment Group	Safety	
14.1.6	Prior Medications by Treatment Group	Safety	
14.1.7	Concomitant Medications by Treatment Group	Safety	
14.1.8	Summary of Antiviral Medications Taken During the Study by Treatment Group, Drug Class and Preferred Term	Safety	
14.2.1	Summary Statistics for Electronic Diary Compliance After Maintenance Dose by Treatment Group	mITT	
14.2.2.1	Descriptive Summary of Overall Lesion Rates by Treatment Group and Observation Period	mITT	x
14.2.2.2	Descriptive Summary of Overall Lesion Rates by Treatment Group and Observation Period	PP	
14.2.3.1	Descriptive Summary of Individual Subject Lesion Rates by Treatment Group and Observation Period	mITT	x
14.2.3.2	Descriptive Summary of Individual Subject Lesion Rates by Treatment Group and Observation Period	PP	

Table No.	Table Title	Analysis Population	IA
14.2.4.1	Frequency of Recurrences at 6 Months After Maintenance Dose by Treatment Group	mITT	x
14.2.4.2	Frequency of Recurrences at 6 Months After Maintenance Dose by Treatment Group	PP	
14.2.5.1	Proportion of Subjects Who Are Recurrence Free at 6 Months After Maintenance Dose	mITT	x
14.2.5.2	Proportion of Subjects Who Are Recurrence Free at 6 Months After Maintenance Dose	PP	
14.2.6.1	Time to First Recurrence After Maintenance Dose	mITT	x
14.2.6.2	Time to First Recurrence After Maintenance Dose	PP	
14.2.7.1	Descriptive Summary and Analysis of Mean Lesion Outbreak Duration Over 6 Months After Maintenance Dose	mITT	x
14.2.7.2	Descriptive Summary and Analysis of Mean Lesion Outbreak Duration Over 6 Months After Maintenance Dose	PP	
14.2.8.1	Summary of Antiviral Medication Use After Maintenance Dose	mITT	
14.2.8.2	Summary of Antiviral Medication Use After Maintenance Dose	PP	
14.3.1.1	Frequency Table of All Adverse Events by SOC, Preferred Term, and Treatment	Safety	
14.3.1.2	Frequency Table of All Adverse Events by SOC, Preferred Term, Treatment, and Severity	Safety	
14.3.1.3	Frequency Table of All Adverse Events by SOC, Preferred Term, Treatment, and Causality	Safety	

Table No.	Table Title	Analysis Population	IA
14.3.1.4	Frequency Table of All Adverse Events Leading to Discontinuation of Dosing by SOC, Preferred Term and Treatment	Safety	
14.3.1.5	Frequency Table of Subjects with Adverse Events of Special Interest by SOC, Preferred Term, and Treatment	Safety	
14.3.1.6	Frequency Table of All Adverse Events with $\geq 5\%$ Occurrence by SOC, Preferred Term, and Treatment	Safety	
14.3.1.7	Summary of Local Reactions and Systemic Events Occurring Within 7 Days Postdose by Treatment and Maximum Severity	Safety	
14.3.1.8	Descriptive Summary of Duration (days) of Systemic Events and Local Reactions by Treatment	Safety	
14.3.1.9	Summary of Antipyretic/Analgesic Medications Taken Within 7 Days after Maintenance Dose by Treatment Group, Drug Class, and Preferred Term	Safety	
14.3.2.1	Frequency Table of Subjects with Serious Adverse Events by SOC, Preferred Term, and Treatment	Safety	
14.3.2.2	Frequency Table of Subjects with Medically Attended Adverse Events by SOC, Preferred Term, and Treatment	Safety	

**Table 14.1.1: Number and Percentage of Enrolled Subjects by Site and Treatment Group**

Safety Population		
Site	GEN-003 60 ug/ M2 50 ug N=xx	Placebo N=xx
Site 1	n (x.x%)	n (x.x%)
Site 2	n (x.x%)	n (x.x%)
Site 3	n (x.x%)	n (x.x%)
Site 4	n (x.x%)	n (x.x%)
etc.		
Site X	n (x.x%)	n (x.x%)
All Sites	n (x.x%)	n (x.x%)

Program:

Date Produced: mm/dd/yy

**Table 14.1.2: Demographic and Baseline Characteristics by Treatment Group**  
 Safety Population

	GEN-003 60 ug/ M2 50 ug N=xx	Placebo N=xx	Total N=xx
Variable			
Age (years)			
n	xx	xx	xx
Mean	xx.x	xx.x	xx.x
SD	xx.xx	xx.xx	xx.xx
Median	xx.x	xx.x	xx.x
Min, Max	xx, xx	xx, xx	xx, xx
Sex			
Male	n (x.x%)	n (x.x%)	n (x.x%)
Female	n (x.x%)	n (x.x%)	n (x.x%)
Race			
American Indian or Alaska Native	n (x.x%)	n (x.x%)	n (x.x%)
Asian	n (x.x%)	n (x.x%)	n (x.x%)
Black	n (x.x%)	n (x.x%)	n (x.x%)
Hawaiian or Pacific Islander	n (x.x%)	n (x.x%)	n (x.x%)
White	n (x.x%)	n (x.x%)	n (x.x%)
Other	n (x.x%)	n (x.x%)	n (x.x%)
Ethnicity			
Hispanic or Latino	n (x.x%)	n (x.x%)	n (x.x%)
Not Hispanic or Latino	n (x.x%)	n (x.x%)	n (x.x%)
Weight (lbs)			
n	xx	xx	xx
Mean	xx.xx	xx.xx	xx.xx
SD	xx.xxx	xx.xxx	xx.xxx
Median	xx.xx	xx.xx	xx.xx
Min, Max	xx.x, xx.x	xx.x, xx.x	xx.x, xx.x

Program:  
 [Sponsor]  
 Protocol: [Protocol number]

Date Produced: mm/dd/yy

page x of y

**Table 14.1.3: Summary of Analysis Populations by Treatment Group**

Population	GEN-003 60 ug/ M2 50 ug N=xx	Placebo N=xx
Modified Intent-to-Treat[a]	n (x.x%)	n (x.x%)
Safety[b]	n (x.x%)	n (x.x%)
Per Protocol[c]	n (x.x%)	n (x.x%)

[a] Includes all randomized subjects who received the maintenance dose.
[b] Includes all randomized subjects who received the maintenance dose.
[c] Includes all subjects in the mITT Population who reported 80% of daily electronic reporting data, and who had no major protocol deviations

Program:

Date Produced: mm/dd/yy

**Table 14.1.4: Subject Disposition by Treatment Group**  
 Safety Population

Disposition	GEN-003 60 ug/ M2 50 ug N=xx	Placebo N=xx
Subject completed the study	n (x.x%)	n (x.x%)
Primary Reason for Discontinuation from Study		
Withdrew consent for reason other than AE	n (x.x%)	n (x.x%)
Withdrew consent due to solicited or unsolicited AEs		
Lost to Follow-up	n (x.x%)	n (x.x%)
Non-compliance	n (x.x%)	n (x.x%)
Investigator discretion	n (x.x%)	n (x.x%)
Sponsor request	n (x.x%)	n (x.x%)
Death	n (x.x%)	n (x.x%)
Site termination	n (x.x%)	n (x.x%)
Study termination	n (x.x%)	n (x.x%)

Program:

Date Produced: mm/dd/yy

**Table 14.1.5: Frequency of Medical History Events by Treatment Group**  
 Safety Population

Medical History Events	GEN-003 60 ug/ M2 50 ug N=xx	Placebo N=xx
SOC1	n (x.x%)	n (x.x%)
Preferred Term for MH Event1	n (x.x%)	n (x.x%)
Preferred Term for MH Event2	n (x.x%)	n (x.x%)
Preferred Term for MH Event3	n (x.x%)	n (x.x%)
SOC2	n (x.x%)	n (x.x%)
Preferred Term for MH Event4	n (x.x%)	n (x.x%)
Preferred Term for MH Event5	n (x.x%)	n (x.x%)
Preferred Term for MH Event6	n (x.x%)	n (x.x%)
SOC3	n (x.x%)	n (x.x%)
Preferred Term for MH Event7	n (x.x%)	n (x.x%)
Preferred Term for MH Event8	n (x.x%)	n (x.x%)
ETC...		

Program:

Programming Notes:

- Data comes from Medical History module
- Sort by SOC and preferred terms
- These data will be coded in MedDRA.

Date Produced: mm/dd/yy

**Table 14.1.6: Prior Medications by Treatment Group**  
 Safety Population

ATC Text Level 2 Preferred Name	GEN-003 60 ug/ M2 50 ug N=xx	Placebo N=xx
ATC Text Level 2	n (x.x%)	n (x.x%)
Preferred Name1	n (x.x%)	n (x.x%)
Preferred Name2	n (x.x%)	n (x.x%)
Preferred Name3	n (x.x%)	n (x.x%)
ATC Text Level 2	n (x.x%)	n (x.x%)
Preferred Name1	n (x.x%)	n (x.x%)
Preferred Name2	n (x.x%)	n (x.x%)
Preferred Name3	n (x.x%)	n (x.x%)
ATC Text Level 2	n (x.x%)	n (x.x%)
Preferred Name1	n (x.x%)	n (x.x%)
Preferred Name2	n (x.x%)	n (x.x%)
Preferred Name3	n (x.x%)	n (x.x%)

Note: Prior Medication mapping was based on WHODRUG.

Program:

Date Produced: mm/dd/yy

Programming Note:

- Prior medications are those medications with a start date BEFORE date of maintenance dose (Day 1).

**Table 14.1.7: Concomitant Medications by Treatment Group**  
 Safety Population

ATC Text Level 2 Preferred Name	GEN-003 60 ug/ M2 50 ug N=xx	Placebo N=xx
ATC Text Level 2	n (x.x%)	n (x.x%)
Preferred Name1	n (x.x%)	n (x.x%)
Preferred Name2	n (x.x%)	n (x.x%)
Preferred Name3	n (x.x%)	n (x.x%)
ATC Text Level 2	n (x.x%)	n (x.x%)
Preferred Name1	n (x.x%)	n (x.x%)
Preferred Name2	n (x.x%)	n (x.x%)
Preferred Name3	n (x.x%)	n (x.x%)
ATC Text Level 2	n (x.x%)	n (x.x%)
Preferred Name1	n (x.x%)	n (x.x%)
Preferred Name2	n (x.x%)	n (x.x%)
Preferred Name3	n (x.x%)	n (x.x%)

Note: Concomitant Medication mapping was based on WHODRUG.

Program:

Date Produced: mm/dd/yy

Programming Note:

- Concomitant medications are those medications with a start date on or after date of maintenance dose (Day 1), or with a start date before Day 1 and continue beyond Day 1.

**Table 14.1.8: Summary of Antiviral Medications Taken During the Study by Treatment Group, Drug Class and Preferred Term**

Safety Population  
Day 1 to Month 6

Preferred Term	GEN-003 60 ug/ M2 50 ug N=xx	Placebo N=xx
Any Antiviral Medication	n (x.x%)	n (x.x%)
Preferred Term 1	n (x.x%)	n (x.x%)
Preferred Term 2	n (x.x%)	n (x.x%)
Preferred Term 3	n (x.x%)	n (x.x%)
etc.		

Program:

Date Produced: mm/dd/yy

Programming Notes:

- Antiviral medications are defined as medications with an ATC2 Class of 'ANTIVIRALS FOR SYSTEMIC USE'

[Sponsor]

Protocol: [Protocol number]

page x of y

**Table 14.2.1: Summary Statistics for Electronic Diary Compliance After Maintenance Dose by Treatment Group**

mITT Population

	GEN-003 60 ug/ M2 50 ug N=xx	Placebo N=xx
Days with Entry		
n	xx	xx
Mean	xx.xx	xx.xx
SD	xx.xxx	xx.xxx
Median	xx.xx	xx.xx
Min, Max	xx.x, xx.x	xx.x, xx.x
Days without Entry		
n	xx	xx
Mean	xx.xx	xx.xx
SD	xx.xxx	xx.xxx
Median	xx.xx	xx.xx
Min, Max	xx.x, xx.x	xx.x, xx.x
Percent Compliance		
n	xx	xx
Mean	xx.xx	xx.xx
SD	xx.xxx	xx.xxx
Median	xx.xx	xx.xx
Min, Max	xx.x, xx.x	xx.x, xx.x

Note: Days with Entry are days from Day 1 to Month 6 visit or date of discontinuation with an entry of 'Yes' or 'No'  
Days without Entry are days from Day 1 to Month 6 visit or date of discontinuation with an entry of blank

Program:

Date Produced: mm/dd/yy

Programming Notes:

- Use Day 1 as start date
- Use earliest of Month 6 visit and date of completion or early termination (dsdtdat) from Subject Disposition form as cutoff date
- Percent Compliance = Days with Entry / (Days with Entry + Days without Entry) \* 100%

[Sponsor]

Protocol: [Protocol number]

page x of y

**Table 14.2.2.1: Descriptive Summary of Overall Lesion Rates by Treatment Group and Observation Period**

mITT Population		
Variable Visit Statistic	GEN-003 60 ug/ M2 50 ug N=xx	Placebo N=xx
Overall lesion rate (days)		
Days with lesions/followup time(%)		
Baseline	xx/xx (%)	xx/xx (%)
Days 1-183	xx/xx (%)	xx/xx (%)

Note: Lesion rate (days) is defined as number of days with lesions divided by the number of days in the observation period.

Note: The overall rate is presented where numerator and denominator are summed across subjects.

Program:

Date Produced: mm/dd/yy

Programming Notes:

- Present results for Baseline and Days 1-183.
- A day with lesions is a day for which LESIONS='Yes'.
- Number this table 14.2.2.1 and produce a similar table (14.2.2.2) for the PP population

**Table 14.2.3.1: Descriptive Summary of Individual Subject Lesion Rates by Treatment Group and Observation Period**

mITT Population		
Visit Statistic	GEN-003 60 ug/ M2 50 ug N=xx	Placebo N=xx
Baseline		
n	xx	xx
Mean	xx.xx	xx.xx
SD	xx.xxx	xx.xxx
Median	xx.xx	xx.xx
Min, Max	xx.x, xx.x	xx.x, xx.x
Total subjects w/ at least 1 day of lesions	n (%)	n (%)
Days 1-183		
n	xx	xx
Mean	xx.xx	xx.xx
SD	xx.xxx	xx.xxx
Median	xx.xx	xx.xx
Min, Max	xx.x, xx.x	xx.x, xx.x
Total subjects w/ at least 1 day of lesions	n (%)	n (%)
Change from Baseline (Days 1-183)		
n	xx	xx
Mean	xx.xx	xx.xx
SD	xx.xxx	xx.xxx
Median	xx.xx	xx.xx
Min, Max	xx.x, xx.x	xx.x, xx.x
P-Value (vs. Placebo) [1]	0.xxxx	

Note: Lesion rate (days) is defined as number of days with lesions divided by the number of days in the observation period.

[1]P-value based on Wilcoxon rank sum test.

Program:

Date Produced: mm/dd/yy

Programming Notes:

- Present results for Baseline and Days 1-183.
- A day with lesions is a day for which LESIONS='Yes'.
- Number this table 14.2.3.1 and produce a similar table (14.2.3.2) for the PP population

[Sponsor]

Protocol: [Protocol number]

page x of y

**Table 14.2.4.1: Frequency of Recurrences at 6 Months After Maintenance Dose by Treatment Group**  
mITT Population

Statistic	GEN-003 60 ug/ M2 50 ug N=xx	Placebo N=xx	P-value[1]
Number of Recurrences at 6 Months after Maintenance Dose			0.xxxx
n	xx	xx	
Mean	xx.xx	xx.xx	
SD	xx.xxx	xx.xxx	
Median	xx.xx	xx.xx	
Min, Max	xx.x, xx.x	xx.x, xx.x	

Note: Recurrences refer to subject-reported recurrences.  
[1]P-value based on Wilcoxon rank sum test.

Program:

Date Produced: mm/dd/yy

Programming Notes:

- Number this table 14.2.4.1 and produce a similar table (14.2.4.2) for the PP population

[Sponsor]

Protocol: [Protocol number]

page x of y

**Table 14.2.5.1: Proportion of Subjects Who Are Recurrence Free at 6 Months After Maintenance Dose**

mITT Population			
Variable Statistic	GEN-003 60 ug/ M2 50 ug N=xx	Placebo N=xx	P-value[1]
Recurrence Free at 6 Months after Maintenance Dose*			0.xxxx
Yes	n (%)	n (%)	
No	n (%)	n (%)	
Unknown	n (%)	n (%)	

\* 'Yes' includes subjects who do not have a recurrence from Maintenance Dose through 6 months after Maintenance Dose.

'No' includes subjects who do have a recurrence from Maintenance Dose through 6 months after Maintenance Dose.

'Unknown' includes subjects who discontinue prior to 6 months after Maintenance Dose and have not had a recurrence prior to discontinuation.

[1] From a chi-square test of homogeneity of proportions (excluding Unknown counts).

Program:

Date Produced: mm/dd/yy

Programming Notes:

- Number this table 14.2.5.1 and produce a similar table (14.2.5.2) for the PP population

**Table 14.2.6.1: Time to First Recurrence After Maintenance Dose**  
 mITT Population

Statistic	GEN-003 60 ug/ M2 50 ug N=xx	Placebo N=xx
Number with recurrence (%)	xx (xx.x)	xx (xx.x)
Number Censored (%)	xx (xx.x)	xx (xx.x)
Time to first recurrence*		
25 th Percentile (95% CI)	xx (xx.x, xx.x)	xx (xx.x, xx.x)
Median (95% CI)	xx (xx.x, xx.x)	xx (xx.x, xx.x)
75 th Percentile (95% CI)	xx (xx.x, NE)	xx (xx.x, NE)
Min, Max	xx, xx	xx, xx
K-M Estimate[1] (95% CI)	x.xxx (x.xxx, x.xxx)	x.xxx (x.xxx, x.xxx)
Log rank test vs. Placebo p-value	0.xxxx	

\* The number of days from Maintenance Dose to the day the subject experienced a recurrence, or the censoring day that the subject was last known to be recurrence-free.

NE = Not Estimable CI = Confidence Interval K-M = Kaplan-Meier

[1] Percent of event-free subjects

Program:

Date Produced: mm/dd/yy

Programming Notes:

- Number this table 14.2.6.1 and produce a similar table (14.2.6.2) for the PP population

[Sponsor]

Protocol: [Protocol number]

page x of y

**Table 14.2.7.1: Descriptive Summary and Analysis of Mean Lesion Outbreak Duration Over 6 Months After Maintenance Dose**

mITT Population

Visit Statistic	GEN-003 60 ug/ M2 50 ug N=xx	Placebo	P-value [1]
6 Months After Maintenance Dose			0.xxxx
n	xx	xx	
Mean	xx.xx	xx.xx	
SD	xx.xxx	xx.xxx	
Median	xx.xx	xx.xx	
Min, Max	xx.x, xx.x	xx.x, xx.x	
Total subjects w/ at least 1 day of lesions	n (%)	n (%)	

Note: Mean lesion outbreak duration is defined for each subject as the average number of days with lesions per outbreak (recurrence) during the period of interest. Subjects with no recurrences during the period of interest are excluded from the analysis.

[1]P-value based on Wilcoxon rank sum test.

Program:

Date Produced: mm/dd/yy

Programming Notes:

- A day with lesions is a day for which LESIONS='Yes'.
- Number this table 14.2.7.1 and produce a similar table (14.2.7.2) for the PP population

[Sponsor]  
Protocol: [Protocol number]

page x of y

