From Month 2 to Month 12, the investigational site will contact each subject by telephone or site visit for review of daily electronic reporting tool data and assessment of SAEs, AESIs, and antiviral medication (through Month 6).

A Data Monitoring Committee (DMC) will review safety data at intervals of a minimum of 3 months until all subjects have completed the GEN-003/placebo dosing period. Any additional meetings and the specific safety monitoring plan will be detailed in the DMC charter.

Efficacy Endpoints:

Primary:

- Genital herpes lesion rate (proportion of days with lesions present) in the 6-month period after the maintenance dose: Based on subject report of genital lesions via a daily electronic reporting tool

Secondary:

- Frequency of genital herpes recurrences in the 6-month period after the maintenance dose: Based on subject report of genital lesions via a daily electronic reporting tool
- Proportion of subjects genital herpes recurrence-free at 6 months after the maintenance dose: Based on subject report of genital lesions via a daily electronic reporting tool
- Time to first genital herpes recurrence in the 6-month period after the maintenance dose: Based on subject report of genital lesions via a daily electronic reporting tool
- Duration of genital herpes recurrences in the 6-month period after the maintenance dose: Based on subject report of genital lesions via a daily electronic reporting tool

Safety Endpoints:

- Reactogenicity
 - Local reactions: Pain, tenderness, swelling, redness
 - Systemic events: Fever, headache, chills, fatigue, nausea, vomiting, diarrhea, muscle aches
- AE, SAEs, AESIs, MAAEs

Number of Subjects Planned: Up to 90 subjects

Diagnosis and Main Criteria for Inclusion: Subjects who completed Study GEN-003-003 (completed all study visits including the Month 12 visit) and received all 3 doses of active GEN-003 (any dose combination), received the last dose of GEN-003 within 11 to 18 months, and reported data in daily electronic reporting period on at least 80% of days, and had no important protocol deviation.

Duration of Treatment: 1 dose

Test Product; Dose; and Mode of Administration: GEN-003 (60 µg of each antigen, GB208)

and GB217, 50 µg of MM2, and normal saline), administered as a 0.5 mL IM injection

Control Product; Dose; and Mode of Administration: Normal saline, administered as a 0.5 mL IM injection

Statistical Methods:

Sample Size: No formal sample size calculations were performed for this study.

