A total of 131 subjects were enrolled, and an interim analysis of data through 6 months postdose was conducted in December 2016 and January 2017. In this analysis, the 60 µg each GEN-003 antigen/50 µg MM2 dose reduced the rate of genital HSV-2 lesions during the 6 months after dosing compared to placebo (4.5% of days vs. 7.9%, respectively; 41% reduction vs. placebo, $P < 0.05$). GEN-003 also consistently demonstrated significant benefits compared to placebo for the secondary clinical endpoints (Table 1).

Table 1: Study GEN-003-003: Secondary Clinical Endpoints – Interim Analysis at 6 Months Postdose

Endpoint	Dose		
	Placebo N = 44	60 µg each GEN-003 antigen/50 µg MM2 N = 43	60 µg each GEN-003 antigen /75 µg MM2 N = 44
Mean duration of recurrences (days) P -value versus placebo ^a	4.8 NA	3.3 0.01	4.3 0.64
Mean number of recurrences over 6 months P -value versus placebo ^a	2.7 NA	2.1 0.08	1.9 0.02
Proportion of subjects recurrence-free 6 months after first dose (Kaplan-Meier estimate) P -value versus placebo ^b	10% NA	29% 0.03	31% 0.02
Proportion of subjects recurrence-free 6 months after last dose (Kaplan-Meier estimate) P -value versus placebo ^b	13% NA	22% 0.17	36% 0.02
Abbreviations: NA = not applicable. a by Wilcoxon rank sum test b by log-rank test			

Overall shedding rates decreased from baseline in both vaccine dose groups. For the 60 µg GEN-003 antigens/50 µg MM2 group, both the decrease from baseline ($P = 0.03$) and the difference from the placebo group ($P = 0.05$) were statistically significant. These differences did not reach statistical significance for the 60 µg GEN-003 antigens/75 µg MM2 group.

IgG geometric mean titers (GMTs) to GB208 and GB217 and HSV-2 neutralizing antibodies increased after dosing in both active vaccine groups, peaking after Dose 1 for GB208 and Dose 3 for GB217 and HSV-2 neutralizing antibody. All post-treatment GMTs in both active vaccine groups were statistically higher than those in the same group at baseline (Day 1) and those in the placebo group at each corresponding time point.

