#### **3.2 Secondary Efficacy Objectives**

The secondary efficacy objectives are as follows:

- To evaluate the efficacy of GEN-003 versus placebo administered as a maintenance dose on genital herpes recurrence through Month 6:
- Reduction of genital herpes recurrence frequency
- Increase of proportion of subjects who are genital herpes recurrence-free
- Increase of time to first genital herpes recurrence
- Reduction of genital herpes recurrence duration

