### **5.2 Sample Size Justification**

Sample size in this study is dependent on the enrollment in GEN-003-003. No formal sample size calculations were performed for this study.

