## **11.5 Duration of Genital Herpes Recurrences**

Mean lesion outbreak duration is defined as the average number of days with lesions per outbreak for those who have lesion outbreaks (recurrences).

Mean lesion outbreak duration will be presented in a similar descriptive summary table as done for lesion rate as described above. Individual subject mean outbreak duration will be summarized by treatment arm over 6 months (Days 1 to 183) after the maintenance dose. A Wilcoxon rank sum test will be used to test the hypothesis that the median mean lesion outbreak durations are the same between treatment groups at 6 months after the maintenance dose.

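### The test of recurrence duration compares only subjects who recurred, so its p-value is not a randomised comparison and cannot be read as an effect on duration

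*SAP*

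**What the plan says.** SAP 3.2 lists "Reduction of genital herpes recurrence duration" as a secondary efficacy objective, next to increasing the proportion of subjects who are recurrence-free. SAP 11.5 gives the measure: "Mean lesion outbreak duration is defined as the average number of days with lesions per outbreak for those who have lesion outbreaks (recurrences"). The same section adds the test: "A Wilcoxon rank sum test will be used to test the hypothesis that the median mean lesion outbreak durations are the same" between treatment groups. The note to Table 14.2.7.1 states the analysis set: "Subjects with no recurrences during the period of interest are excluded from the analysis". The list of tables repeats the analysis for the PP population (Table 14.2.7.2) and marks the mITT table for the interim analysis.

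Protocol 10.8.4 names the same Wilcoxon comparison but does not mention the exclusion. Neither document gives a caveat, an estimand or a sensitivity analysis for this endpoint. Table 14.2.7.1 does print n and the number of subjects with at least one lesion day. SAP 11.3 tests the recurrence-free proportion separately, and the primary lesion rate in SAP 11.1 has no such exclusion.

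**The concern.** Randomisation makes the arms comparable at dosing. It does not make the recurrers in one arm comparable with the recurrers in the other when treatment influences who recurs. The plan treats recurrence-free status as an efficacy outcome in one table and as an exclusion rule in another, so the duration test conditions on a result of treatment. The p-value then mixes any change in the length of outbreaks with a change in which subjects and outbreaks remain to be measured.

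At stake is the answer to one secondary objective. A significant difference in either direction, or no difference, could come from selection alone, and nothing in the planned output would separate the two.

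**Working it through.** The plan gives no power, alpha or expected value for this test ("No formal sample size calculations were performed for this study"), so there is no stated figure to reproduce. Two-sided 0.05, that is 2.5% in each direction, is assumed.

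**Inputs from Protocol 1.5.5, Table 1 (parent study).**
- Placebo: mean duration 4.8 days, mean 2.7 recurrences over 6 months.
- Recurrence-free, placebo vs the 60/50 µg dose used here: 10% vs 29% from first dose, 13% vs 22% from last dose.
- These are illustrative only. Table 1 compares vaccinated with unvaccinated subjects, whereas both arms here have already had three active doses.

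**Step 1. Unequal loss.** With up to 90 subjects planned, take 45 per arm. Retained = 45 × (1 − recurrence-free share). Share of would-be recurrers removed = 1 − (1 − active share)/(1 − placebo share).
- 10% vs 29%: 45 × 0.90 = 40.5 and 45 × 0.71 = 32.0 retained; removed 1 − 0.71/0.90 = 21%.
- 13% vs 22%: 45 × 0.87 = 39.2 and 45 × 0.78 = 35.1 retained; removed 1 − 0.78/0.87 = 10%.

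**Step 2. Bias when whole subjects are removed.** Simulation: 45 per arm, 4,000 trials per scenario, per-subject mean durations gamma with mean 4.8 days. The SD is not in the documents, so 1.5, 2.5 and 3.5 were assumed. The vaccine has no effect on duration in anyone who still recurs. Results at 10% vs 29%:

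| Who is prevented from recurring | Active mean (placebo 4.8 days) | Significantly longer | Significantly shorter |
|---|---|---|---|
| Unrelated to duration | 4.8 | 2%-3% | 2%-3% |
| Five times likelier below median duration | 5.0-5.3 | 9%-10% | under 1% |
| Exactly the shortest | 5.3-5.8 | 33%-34% | 0% |
| Exactly the longest | 3.4-4.2 | about 0% | 32%-35% |

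At 13% vs 22%, the shortest-removed case gives 10%-11% significantly longer and the longest-removed case 11%-12% significantly shorter.

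**Step 3. Bias when individual outbreaks are prevented.** Arm size: the parent study put 43 + 44 = 87 subjects on active, and 2 in each active group stopped dosing for safety reasons. At most 87 − 4 = 83 could have had all three doses, so 41 per arm was used. Outbreak counts are overdispersed with mean 2.7, and lengths average 4.8 days. Assumed: between-subject log-SD 0.5, within-subject log-SD 0.3-0.6, and the count dispersion. Outbreaks of 3 days or less are prevented with probability 50% or 75%, and none is lengthened.
- Significantly longer on active: roughly 9%-14% (50%) and 21%-41% (75%).
- Total lesion days: down about 10% and 15%. The loss is proportional to the prevention probability: 10% × 0.75/0.50 = 15%.
- Equal thinning of all outbreaks gives no inflation. Preventing long outbreaks gives 7%-12% falsely shorter.

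The rates depend strongly on the variances. With 45 per arm and outbreak lengths that do not differ systematically between subjects (SD 2.5 days), the 75% scenario gave 60%.

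**Step 4. Two routes.** In that last model the mean for all untreated recurrers is 4.81 days. Untreated, those who would remain recurrers have a mean of 5.03; treated, the same subjects have 5.66. Dropped subjects contribute 5.03 − 4.81 = 0.22 days, and averaging only surviving outbreaks contributes 5.66 − 5.03 = 0.63, together 0.85. Most of the shift in this scenario is within retained subjects.

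**Step 5. Effect of keeping everyone.** Scoring recurrence-free subjects 0 in the Step 2 shortest-removed case lowers the significantly-longer rate from 33%-34% to about 1%, with about 7% significantly shorter. In the Step 3 scenarios it falls to 2%-4%. The cost shows under equal thinning, where the zero-scored test gives about 10% significantly shorter although no outbreak's length has changed.

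**The case against.** Duration is undefined without a recurrence, so a recurrers-only summary is the natural description, and the SAP states the exclusion openly and prints n. That stands for the description. It does not justify a between-arm p-value presented as a test of efficacy.

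A reader might infer that the plan would report a working vaccine as lengthening recurrences. The documents do not support that. Nothing in them says short outbreaks are the ones prevented. In Table 1 both active groups had more recurrence-free subjects and a shorter mean duration (3.3 and 4.3 vs 4.8 days). Those means may carry the same selection, since Table 1 does not say how recurrence-free subjects were handled. The direction is unknown, and prevention unrelated to duration gives no bias.

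A reader might also take Table 1's recurrence-free gap as a forecast of unequal loss here. It is not: this trial compares a fourth dose with no fourth dose, and Table 1's largest share, 36% from last dose, belongs to the 75 µg adjuvant group, which is not the dose given in this trial.

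It is also fair that zero scoring changes the question and overlaps with the primary lesion rate, which already combines frequency and duration. That is why the added test needs its own label. Finally, this is one of four secondary endpoints in a phase 2 study whose product development, according to Protocol Appendix 6, has stopped. That limits the stakes.

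**Conclusion.** The point holds as a cheap improvement. The duration p-value compares subsets formed after randomisation by an outcome the vaccine is meant to change, so it cannot be read as a treatment effect on duration, and neither document says so. The size and sign of the bias depend on which outbreaks are prevented, which the documents do not show. In the scenarios examined, a falsely significant result in one direction ranged from the nominal 2.5% to about a third when whole subjects are removed. It was roughly 9%-14% or 21%-41% when 50% or 75% of short outbreaks are prevented, and 60% under one other variance assumption. All of these rest on assumed variances, an assumed alpha and parent-study placebo rates from a different contrast; they illustrate the mechanism and predict nothing about this trial. The primary lesion-rate analysis does not use this exclusion.

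**What to change.** In SAP 11.5 and Tables 14.2.7.1 and 14.2.7.2:

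- Report recurrers-only durations descriptively, labelled as conditional on recurrence and not as a randomised efficacy test.
- Add an all-mITT Wilcoxon test in which subjects known to be recurrence-free through Month 6 take the lowest rank, labelled as a composite of prevention and shortening.
- State a separate rule for early discontinuers without a recurrence, whom Table 14.2.5.1 already classes as *Unknown*. For example, exclude them and add a sensitivity analysis. Do not score them 0, which would give dropouts the best rank.

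The cost is SAP wording and a small programming change, with no new data. The downside is that the tested measure is no longer pure duration and overlaps with lesion rate. Zero scoring brings the false significantly-longer rate to about nominal or below, but it does not correct the recurrers-only means, which still average only surviving outbreaks and need the caveat.
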